### 5.7.2 Clinical laboratory

The following laboratory safety data are collected for this study:

Hematology	Chemistry	Urinalysis	Other
Haematocrit (HCT)	Bilirubin (direct) and Bilirubin (total)	Blood	Serum β-human chorionic gonadotropin (β-hCG)
Haemoglobin (HGB)	Alkaline phosphatase	Glucose	Hepatitis B surface antigen (HBsAg)
RBC	Alanine aminotransferase (ALT)	Protein	Hepatitis C virus antibody (HCV-Ab)
Platelet count	Aspartate aminotransferase (AST)	Specific gravity	HIV antibody (HIV-Ab)
WBC	Bicarbonate	Microscopic exam, if abnormal results are noted	Plasma vitamin B6 levels
Differential count:	Calcium	Ketone	Cystatin C
- Basophils	Chloride	PH	
- Eosinophils	Creatinine	Nitrite	
- Lymphocytes	GammaGT (GGT)	Leukocytes	
- Monocytes	Fasting Glucose	Bilirubin	
- Neutrophils	Potassium	Urobilinogen	
	Sodium		
	Uric Acid		
	Total protein		
	Urea (BUN)		
	eGFR		
	Activated partial thromboplastin time (aPTT)		
	Protrombin Time (PTT)		
	Fibrinogen		
	Lactate dehydrogenase (LDH)		
	Creatinine kinase (CK)		

Laboratory safety data will be summarized using descriptive statistics over time, and listed per visit and treatment group, using protocol visits. Change from baseline will be calculated and

presented as well for quantitative data, using the same summary statistics. The categorical data of urinalysis will be summarized by treatment and time in frequency tables by variable. If applicable, laboratory safety data collected as additional/unscheduled assessments (i.e. apart from those per protocol) will only be listed and will not be used in summary statistics.

For laboratory safety data, all recorded and determined laboratory safety data will be listed. Safety laboratory parameters will be presented in the tables and listings in the same (standardized) units as supplied. Since data will be provided in both conventional as SI units, SI units will be used for presentation purposes.

It should be noted that Creatinine and Creatinine Kinase are also part of the Biomarker analysis and will therefore be presented twice for different analysis populations.

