#### ***Rationale for vitamin B6 monitoring and Nerve Conduction Study***

Axonal degeneration as observed in non-clinical studies (Schoenmakers A., 2019) are possibly related to reduced levels of pyridoxal 5'-phosphate (PLP) in plasma, the active form of vitamin B6 (CHMP EMA, 2019). In the clinic similar axonal damage has been associated with a decrease of vitamin B6. This was observed with tuberculosis therapy with the antibiotic isoniazid. Accordingly, supplementation with vitamin B6 is generally recommended during isoniazid therapy. The scientific rationale for reduction of vitamin B6 with edaravone treatment has been established (CHMP EMA, 2019), and therefore, during this study vitamin B6 levels will be monitored and, if necessary, supplementation of vitamin B6 with pyridoxine (maximal 100 mg/day) will be prescribed.

In addition, to allow early detection of neurotoxicity during treatment with FAB122, Nerve Conduction Study (NCS) will be performed at screening, week 4, week 12, and week 24, and DSMB interim assessment on vitamin B6, clinical signs, ALSFRS-R questions related to leg functioning (8. walking and 9. climbing stairs) and NCS data when 60 subjects (about 40 active and 20 placebo) have been treated for 24 weeks:

- a. If no neurological concerns are observed, the study will continue with one additional NCS at week 48;
- b. If NCS show signs of neurological damage, intensive NCS monitoring will continue every 12 weeks for all patients. All NCS measurements will be centrally analysed by an independent neurophysiologist from the Neuromuscular center, UMC Utrecht, The Netherlands.

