5. The DSMB will assess the results of the NCS for the first enrolled 60 patients (about 40 active and 20 placebo). The NCS will be conducted for the first enrolled 60 patients at screening, and on weeks 4, 12, and 24. Then according to the evaluation by the DSMB, one of the following options will be performed: 1) If no neurological concerns are observed, the study will continue with one additional NCS at week 48 for the first 60 patients. Then for the next enrolled patients, one NCS will be performed at Screening and another one at week 48. Additional NCS(s) could be performed between Screening and week 48 if any abnormality is detected by the neurological examination or any suggesting symptoms of neuropathy are reported by the patient. 2) If NCS show signs of neurological damage, intensive NCS monitoring will continue for all patients at Screening and on weeks 4, 12, 24, 36, 48, 60, and 72.
6. Hematology: hematocrit, hemoglobin, RBC (red blood cell count & parameters), WBC (white blood cell count inclusive differential count), platelet count. Biochemistry: total protein, alkaline phosphatase, AST (aspartate transaminase), ALT (alanine transaminase), GGT (Gamma-glutamyl transpeptidase).

direct and total bilirubin, blood urea nitrogen (BUN), creatinine (serum), sodium, potassium, chloride, calcium, bicarbonate, LDH (lactate dehydrogenase), CK (creatinine kinase), eGFR (estimated glomerular filtration rate), uric acid, aPTT, PTT, fibrinogen and fasting glucose. Cystatin C

7. Vitamin B6 levels will be monitored and, if necessary, supplementation of vitamin B6 (pyridoxine (100 mg/day)) will be prescribed.

8. Urinalysis: Blood, Glucose, Protein, Specific gravity, Ketone, pH, Nitrite, Leukocytes, Bilirubin, Urobilinogen, Microscopic exam, if abnormal results are noted.

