### 6.3. Subsequent Visits

#### Visit 2 Week 4 (Day 28 ±3Days)

The following procedures will be performed:

- Review ongoing concomitant medications
- Neurological examination
- Vital signs measured with the subject in a supine/semi-supine position (for at least 5 minutes prior), including blood pressure, pulse rate, pulse oximetry and temperature
- Fasting blood samples for routine clinical labs (clinical chemistry, haematology). See table 2 for lab assessments
- Urine samples for urinalysis
- Plasma vitamin B6 levels, and, if necessary, vitamin B6 supplements (pyridoxine (100 mg/day)) will be prescribed.
- ALS evaluation procedures: ALSFRS-R
- Blood sampling for biomarker: neurofilament light (NFL). Creatinine and creatine kinase will be measured in routine biochemistry lab testing.

- Urine collection for biomarkers: urinary extracellular domain of neurotrophin receptor p75 (Urinary P75ECD) and oxidative stress biomarker 8-hydroxyguanosine (8-OHdG)
- Blood sampling for FAB122, in selected sites if consented
- Blood sampling for riluzole, in selected sites if consented
- Nerve Conduction Study (NCS)
- Adverse Events monitoring
- Compliance check

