14.2.16.2	Statistical analysis results for HDD mega score	
14.2.17.1- 14.2.17.6	Descriptive statistics for Quality of Life: ALSAQ-40 (total score and 5 scales)	
14.2.17.7	Statistical analysis results for Quality of Life: ALSAQ-40 total score	
14.2.17.8	Descriptive statistics for Quality of Life: EQ-5D-5L	
14.2.17.9	Descriptive statistics for Quality of Life: VAS	
14.2.17.10	Statistical analysis results for Quality of Life: VAS	
14.2.18.1- 14.2.18.x	Descriptive statistics for Cognition (ECAS)	
14.2.19.1- 14.2.19.x	Descriptive statistics for Biomarkers	
14.2.19.5	Out of range Biomarkers	

14.2.20.1- 14.2.20.x	Descriptive statistics for Cost-Utility analysis	
14.3 Safety Data Summary figures and tables – 14.3.1 Displays of Adverse Events		
14.3.1.1	Overview adverse events	X
14.3.1.2	Treatment emergent adverse events	X
14.3.1.3- 14.3.1.5	Treatment emergent adverse events by severity	X
14.3.1.6- 14.3.1.7	Treatment emergent adverse events by relationship	X
14.3.1.8	Treatment emergent adverse events leading to premature discontinuation	X
14.3.1.9	AESIs	X
14.3.1.10	SAEs	X
14.3 Safety Data Summary figures and tables – 14.3.2 Listings of Deaths, Other Serious and Significant Adverse Events		
14.3.2.1	AESIs	
14.3.2.2	SAEs	
14.3.2.3	Deaths	
14.3 Safety Data Summary figures and tables – 14.3.4 Abnormal Laboratory Value Listing (each patient)		
14.3.4.1	Out of range clinical laboratory	
14.3.4.2- 14.3.4.7	Descriptive statistics Clinical laboratory – haematology, clinical chemistry, urinalysis, serology, vitamin B6	
14.3.4.8.1	Descriptive statistics Vital signs	
14.3.4.8.2	Mean (SD) plot Vital signs	
14.3.4.9.1	Descriptive statistics ECG	
14.3.4.9.2	Mean (SD) plot ECG	
14.3.4.10	Physical Examination	
14.3.4.11.1- 14.3.4.11.x	Nerve Conduction Study	
14.3.4.12- 14.3.4.13	Prior and concomitant medication	

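### Vitamin B6 is summarised by visit without separating values taken after on-study pyridoxine, so a fall on FAB122 may be understated from the visit after supplementation starts

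*SAP*

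**What the plan says.** Protocol 2.1 (rationale for vitamin B6 monitoring and NCS) gives the reason for measuring B6: "The scientific rationale for reduction of vitamin B6 with edaravone treatment has been established". It continues that "during this study vitamin B6 levels will be monitored and, if necessary, supplementation of vitamin B6 with pyridoxine (maximal 100 mg/day) will be prescribed". Note 7 to Protocol Table 1 and the visit lists in 6.1 to 6.3 repeat the instruction at screening, baseline and every later clinic visit; at Week 4, for example: "Plasma vitamin B6 levels, and, if necessary, vitamin B6 supplements (pyridoxine (100 mg/day)) will be prescribed". No trigger level is given.

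SAP 5.7.2 places plasma vitamin B6 among the laboratory safety data. The rule for all of these is "Laboratory safety data will be summarized using descriptive statistics over time, and listed per visit and treatment group, using protocol visits", with change from baseline for quantitative data. The one stated exclusion is for additional or unscheduled measurements, which "will only be listed and will not be used in summary statistics". SAP 10.3 plans the output as "Descriptive statistics Clinical laboratory – haematology, clinical chemistry, urinalysis, serology, vitamin B6".

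Baseline in SAP 5.1 is the last pre-dose value, whether or not the patient was already supplemented. Pyridoxine use would appear in the general medication tables and listings of SAP 5.7.5, which are not linked to the B6 summary.

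**The concern.** Supplementation here is a response to the variable being tabulated. A patient whose B6 is found low is supplemented, and from the next visit contributes a corrected value. If FAB122 lowers B6, more patients on FAB122 would be expected to cross whatever threshold the sites use, so the arm with more depletion would also hold more corrected values. A by-visit average over supplemented and unsupplemented patients then mixes the drug effect with its treatment.

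Neurotoxicity is the special monitoring concern in Protocol 2.2, and B6 is followed alongside NCS for that reason. A reader of the study report who turns to the B6 table to see whether the drug lowers B6 could be falsely reassured.

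**Working it through.** **Is there a figure in the plan to reproduce?** No. The documents state no B6 level, expected fall, trigger or supplemented share. Every number below is an assumption used to show direction and range.

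**Timing.** B6 is drawn, and pyridoxine prescribed if needed, at the same visit. The low value therefore stays in the table at the visit where it is found, and the corrected value enters at the next one. Post-pyridoxine values enter because no rule in the SAP sets them apart; no sentence says explicitly that they are included.

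**Break-even share.** Let unsupplemented patients fall by a%, supplemented patients rise by b% over baseline, and a share f be supplemented. Mean change = −(1 − f)a + f·b, which is zero at f* = a/(a + b).

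| Fall in unsupplemented (a) | b = 50% | b = 100% | b = 200% |
|---|---|---|---|
| 10% | 10/60 = 16.7% | 10/110 = 9.1% | 10/210 = 4.8% |
| 20% | 20/70 = 28.6% | 20/120 = 16.7% | 20/220 = 9.1% |
| 30% | 30/80 = 37.5% | 30/130 = 23.1% | 30/230 = 13.0% |

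Above these shares the arm mean shows a rise although every unsupplemented patient has fallen.

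**Simulation with both arms under the same rule.** Assumptions: median baseline 100 units; between-patient CV 50%; within-patient CV 20%; pyridoxine started when a measured value, including baseline, is below an illustrative 50 units; supplement multiplies the level by 2, 4 or 8 from the next visit; five post-baseline visits (matching Weeks 4, 12, 24, 36 and 48). The true drug effect is a 20% fall, which without supplementation gives a mean change of about −22 units. Change at visit 5:

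| Supplement factor | FAB122 mean | Mean with no drug effect | Difference | FAB122 median |
|---|---|---|---|---|
| ×2 | −6.9 | +9.8 | −16.7 | −6.7 |
| ×4 | +23.7 | +29.3 | −5.6 | −6.0 |
| ×8 | +84.9 | +68.2 | +16.7 | −6.0 |

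The FAB122 median shrinks from about −17.5 at the first post-baseline visit to about −6 at visit 5. It keeps its sign. At ×8 the median with no drug effect is +7.9, so the difference in medians is −6.0 − 7.9 = −13.9.

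**First post-baseline visit.** At ×4 the FAB122 mean change is −11.5 and 11% are low. The shortfall from −22 comes from the 9.4% already supplemented at baseline. That precedes the drug and affects both arms alike.

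**What a cumulative measure retains.** At ×4, 23.5% of the FAB122 arm have been below the trigger at least once by visit 5, against 10.0% with no drug effect. The by-visit summary at visit 5 shows only 1.8% of the FAB122 arm currently low.

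**The case against.** The strongest reply is that the signal is attenuated, not lost, and that other planned outputs carry it.

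- A reader might infer that the planned table is unable to show a fall in B6. The documents do not support that. Week 4 precedes any pyridoxine prompted by a scheduled on-drug value, so its by-arm comparison is free of drug-triggered supplementation. Later first-low values remain at the visit where they are found, and SAP 5.1 requires the median and minimum as well as the mean.
- A reader might infer that the table would show the opposite of the truth between arms. In the illustration the difference in means reverses only at ×8; at ×2 and ×4 it shrinks but still points to depletion.
- A reader might take B6 loss to be the protocol's settled mechanism for nerve damage. Protocol 2.1 calls the link to axonal degeneration only possible, and Protocol 2.2 names demyelination as the primary effect.
- A reader might infer that NCS findings are left unexplained. Protocol 2.1 and 8.2.5 plan a joint DSMB review of B6, NCS and clinical signs in the first 60 patients, under a separate DSMB SAP that is not among these documents.
- Protocol 9.1.1 makes an abnormal laboratory result an adverse event if it needs treatment, so a treated low B6 should reach the TEAE tables. B6 listing 16.2.7.6, the out-of-range output 14.3.4.1 and the medication listings with dates and reasons allow reconstruction.

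All of this stands as a limit on the point. It does not remove it: the adverse event route depends on site reporting, the DSMB review covers 60 patients to Week 24, and reconstruction from listings is not a planned by-arm result. Pyridoxine may also start before first dose and in either arm, so not every supplemented patient is one the drug has depleted.

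**Conclusion.** The point holds as a reporting gap in a descriptive safety summary. SAP 5.7.2 does not separate B6 values by pyridoxine use, although pyridoxine is given in response to B6. From the visit after supplementation starts, the mean, and less so the median, is biased toward no change or a rise, so a fall on FAB122 may be understated.

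The size cannot be stated. Under the assumed inputs, a true mean change of about −22 units reads between −6.9 and +84.9 within the FAB122 arm at visit 5, and the between-arm difference between −16.7 and +16.7. Real figures depend on how many patients are supplemented, at what level, and how far B6 then rises. No data are lost, and no planned test depends on this table. It is worth correcting because the correction is cheap and B6 is followed for a named safety concern.

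**What to change.** In SAP 5.7.2, with a matching entry in 10.3:

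1. Make the lead B6 display a by-arm table of the cumulative number and percentage of patients who, after first dose, first fall below the laboratory reference limit or start pyridoxine, with time to that event. Flag patients already supplemented before first dose.
2. Keep the by-visit table of all values, and add rows for values before and after first pyridoxine as supportive only. Note beside the pre-pyridoxine row that it progressively loses the most depleted patients; ending each series at first pyridoxine would hide a fall in another way and should not be the main summary.

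The cost is SAP wording and one extra table, from laboratory and concomitant medication data already collected.

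No change to when or how pyridoxine is given is proposed. Separately, Protocol 2.1 states the pyridoxine amount as a maximum while Table 1 and the visit lists state it as a fixed amount; these passages should be reconciled.

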- ALT/AST  $\geq$  5xULN and ALT/AST  $<$  8xULN that persists more than two weeks

8-Acute lung injury with pyrexia, cough, dyspnoea and chest X-ray abnormality

9-Rhabdomyolysis

10-Disseminated intravascular coagulation (DIC)

11-Hypersensitivity reaction

12- Anaphylactic reaction/shock

13- Thrombocytopenia

14- Neutropenia

15-Introduction of riluzole

16-The subject cannot attend two consecutive study visits and key safety assessment cannot be performed

If a subject discontinues the trial for safety reasons, a PK sample is to be taken (with the time of sampling after last dosing clearly documented) in those sites participating in the PK sub study.

In case a subject withdraws FBR consent, the blood samples taken for FBR will be destroyed (when not analysed yet).

The sponsor reserves the right to terminate the study at any time if continuation of the protocol would present a potential safety risk to the subjects.

Every effort will be made to ensure that patients who do not complete all study requirements return to the site for the End-of-Trial Visit. Patients who withdraw due to an Adverse Event (AE) or Serious Adverse Event (SAE) will be given appropriate care under medical supervision until the symptoms resolve or the patient's condition becomes stable. The End-of-Trial Visit will be performed 7-14 days after withdrawal and the same procedures as Visit 8 will be performed.

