### **8.2.2. Laboratory Parameters**

The results of clinical laboratory tests conducted at the screening visit must be assessed by the investigator to determine each subject's eligibility for participation in the study. The results of all clinical laboratory tests conducted during the study must be assessed by the investigator to assess patients' safety.

Any significant abnormalities is to be documented and followed up as AEs and should be fully investigated. Whenever possible, the etiology of the abnormal findings will be documented in the database. Laboratory results with significantly abnormal values should be investigated as such and checked for verification. Additional tests and other evaluations required to establish the significance or etiology of an abnormal result or to monitor the course of an AE should be obtained when clinically indicated. In particular, if a clinically significant abnormal result is observed that is not resolved by the final study visit, repeat tests will be performed if possible and resolution or stability of the abnormality will be recorded in the source documentation.

Any significant laboratory abnormalities that are either serious or unexpected will be promptly reported to the sponsor's Medical Monitor. Any additional relevant laboratory results obtained by the investigator during the course of this study will be reported to the sponsor or its representative.

---

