#### 11.3.6. Safety Analysis

Safety evaluations will be based on the incidence, severity, and type of AEs and clinically significant changes in the subject's physical examination findings, vital signs, and clinical laboratory results. Safety variables will be tabulated and presented for all subjects in the Safety Population. Data will be summarized by treatment and time. Exposure to study drug and reasons for discontinuation of study drug will be tabulated.

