# **5 STATISTICAL ANALYSIS**

## **5.1 General considerations**

Raw data (in listings) will be presented in the same precision as received. Appropriate rounding will be performed for the summary statistics: arithmetic mean, median, SD (standard deviation) and confidence limits will be presented with one more decimal than the original data; minimum and maximum values will be presented with the same precision as the original data. In frequency tables, percentages will be presented with 1 decimal. P-values will be presented with 3 decimals, and those smaller than 0.001 will be replaced by <0.001.

Descriptive statistics presented in general summary tables will be the number of non-missing observations (n), mean, SD, minimum, median and maximum for quantitative data. For categorical data, frequency counts and percentages will be determined. The denominator when calculating percentages will be the number of patients in the applicable analysis population. Descriptive statistics will be displayed for all visits that a measurement is collected on, even if the endpoint is only referring to limited visits for the analysis.

Baseline is defined as the last value measured prior to first study treatment administration, unless otherwise specified. In case this value is missing for a specific patient, but an earlier measurement (e.g. screening) is present, this value will be used as baseline instead. Unscheduled measurements are excluded as baseline value.

If available in the database, data for screening failures will not be presented in summary tables, except for disposition and end-of-study displays. Data for screening failures will be listed as available.

For patients that are unable to attend the clinic on a study visit due to ALS progression, at least ALSFRS score, AEs and concomitant medication data are collected. These data may be collected by telephone and are considered of the same quality as performed during live visits.

If a patient is not able to attend the site for two consecutive visits, then IMP will be discontinued at the 2nd missed visit, but participation in the trial and data collection can continue via telephonic visits to collect ALSFRS-R, AE and concomitant medication. It is assumed that data collected via telephone visits is of same quality as the data collected via site visits.

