### **5.3 Mapping of unscheduled or early termination visits**

When visit assessments are missing, repeat assessments performed within the agreed time window of +/- 7 days will be mapped to the appropriate visit in the database by the DM vendor. Repeat assessments performed outside of these agreed time windows are collected in the database using an unscheduled visit. For these unscheduled assessments following a missing protocol visit, mapping will be done to the (closest) protocol visit at which the applicable assessment should have been performed before the date of unscheduled visit.

In case of a repeated or additional assessments for non-missing assessments, mapping will only be done for replacement if this is clearly agreed (at patient and visit level) with the client and specified by DM vendor (e.g. because it replaces an erroneous measure collected at the actual visit), and as such will be used in statistical data presentations. These agreements will be documented during the BDRM.

For patients that withdraw early from the trial, an early termination visit is scheduled 7-14 days after withdrawal, for which the same procedures as for visit 8 will be performed. The data of this early withdrawal will be mapped to the most appropriate scheduled post-baseline visit as applicable per assessment, to be agreed together with the DM vendor and the client on occurrence. The documentation of these agreements is to be finalized during the BDRM. For early termination visits in general mapping will be done to the closest protocol visit at which the applicable assessment should be performed after the date of early termination.

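### No planned table counts, by arm, the patients who meet the protocol's numeric liver and renal criteria or shows worst post-baseline laboratory values, and unscheduled results not mapped under SAP 5.3 are only listed

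*SAP*

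**What the plan says.** **Summaries.** SAP 5.7.2: "Laboratory safety data will be summarized using descriptive statistics over time, and listed per visit and treatment group, using protocol visits". SAP 5.1 sets the statistics as "the number of non-missing observations (n), mean, SD, minimum, median and maximum for quantitative data". For results outside the schedule, SAP 5.7.2 adds that "additional/unscheduled assessments (i.e. apart from those per protocol) will only be listed and will not be used in summary statistics".

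**Exceptions.** SAP 5.3 sends some off-schedule results into the by-visit summaries. "For these unscheduled assessments following a missing protocol visit, mapping will be done to the (closest) protocol visit" covers missed visits. For results that are not missing, "mapping will only be done for replacement if this is clearly agreed (at patient and visit level) with the client". Early termination samples are generally mapped forward to the next suitable protocol visit. SAP 5.7.2 does not refer to 5.3, and neither section says how the two fit together for laboratory data.

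**Criteria.** Protocol 6.5 lists five ALT/AST-based liver criteria and a Cockcroft-Gault creatinine clearance criterion that require study treatment to stop. One liver criterion is ALT/AST at or above 5xULN and below "8xULN that persists more than two weeks". Thrombocytopenia and neutropenia are also listed, without numeric cut-offs.

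**Repeats and purpose.** Protocol 8.2.2: "Laboratory results with significantly abnormal values should be investigated as such and checked for verification". Protocol 11.3.6 bases the safety evaluation partly on "clinically significant changes in the subject's physical examination findings, vital signs, and clinical laboratory results".

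**Outputs.** SAP 10.3 plans descriptive laboratory tables and one out-of-range laboratory output (14.3.4.1), filed under a heading for per-patient listings of abnormal values. It plans no laboratory shift, worst-value or threshold table. SAP 6 keeps CTCAE grades out of the tabulations. For nerve conduction, SAP 5.7.7 does plan by-arm shift categories and counts of falls of more than 50%.

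**The concern.** The protocol defines laboratory events serious enough to stop study treatment, and the analysis plan has no display that compares the arms on how often they occur. Repeat samples, which confirm such an event or show that it persists, are as a rule only listed.

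A reader of the clinical study report would have to go through listings to find out whether more patients on FAB122 than on placebo met a liver or renal criterion. Liver tests deserve this comparison: protocol 2.2 reports one transient AST rise in trial C1.02 and one transient AST, ALT and GGT rise in the 200 mg cohort of EDV-PBA-01-FRI/20. Adverse events of special interest (protocol 9.1.4) cover neuropathy and nerve conduction only, so that table will not group liver or renal events either.

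**Working it through.** The documents give no figure for how many laboratory excursions the summaries would capture, so there is none to reproduce. The check has two parts.

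**1. What each planned summary can show, criterion by criterion**

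| Protocol 6.5 criterion | What the by-visit summaries show | What is missing |
|---|---|---|
| ALT/AST ≥8xULN | The visit maximum, if the peak falls on a protocol visit or is mapped to one | Number of patients; peaks seen only on unmapped samples |
| ALT/AST ≥3xULN with bilirubin ≥2xULN (>35% direct) | ALT, AST and bilirubin separately | The joint event within a patient |
| ALT/AST 5 to <8xULN for more than two weeks | Separate visits, not linked within patient | Persistence |
| ALT/AST ≥3xULN, or ≥3x baseline, each with symptoms | As in the first row | Number of patients meeting the laboratory part; symptoms are not laboratory data |
| Creatinine clearance <30 mL/min | Creatinine and eGFR | Clearance: neither SAP 5.7.2 nor SAP 9.1 derives it |
| Thrombocytopenia, neutropenia | Platelet and neutrophil summaries | Worst value per patient; there is no numeric cut-off to count against |

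The joint event shows the limit most clearly. Suppose that at one visit one patient has ALT at 3xULN with normal bilirubin, and another has normal ALT with bilirubin at 2xULN. Now move both raised values to the same patient. The mean, SD, minimum, median and maximum of each analyte are unchanged, but the number of patients with both rises goes from 0 to 1.

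**2. Visit spacing**

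Inputs: post-baseline safety samples at weeks 4, 12, 24, 36, 48, 60 and 72 (protocol 6.3; SAP 2.5). The gaps after week 4 are 12 − 4 = 8 weeks, then 12 weeks each. Both far exceed two weeks, and the visit windows of ±3 or ±7 days do not change that. Two consecutive scheduled results in the 5 to <8xULN band would be 8 to 12 weeks apart and could be two separate episodes. A repeat sample between visits is normally what settles the matter. If the scheduled result exists, that repeat is not mapped unless a replacement is specifically agreed.

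The spacing can be described for excursions of an assumed duration L, with onset uniform over weeks 0–48 and visit windows ignored. The gaps are 4, 8, 12, 12 and 12 weeks (total 48).

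Share that includes a scheduled sample = Σ min(gap, L) / 48

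- L = 2 weeks: (2+2+2+2+2)/48 = 10/48 = 21%, so 79% fall between samples.
- L = 4 weeks: (4+4+4+4+4)/48 = 20/48 = 42%, so 58% fall between samples.
- L = 5 weeks: (4+5+5+5+5)/48 = 24/48 = 50%, the break-even.
- L = 8 weeks: (4+8+8+8+8)/48 = 36/48 = 75%, so 25% fall between samples.

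Over weeks 0–72 the shares between samples are 81% (2 weeks: 1 − 14/72) and 61% (4 weeks: 1 − 28/72). These percentages describe the schedule under assumed durations. They do not measure data removed by SAP 5.7.2.

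**The case against.** The case for leaving the plan alone has real substance.

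- **Not everything unscheduled is excluded.** A reader of SAP 5.7.2 alone might infer that every unscheduled result is dropped from every summary. SAP 5.3 does not support that. Patients who stop treatment are also asked back for end-of-trial procedures, which include chemistry and haematology. This stands. However, 5.3 does not ordinarily map a repeat or a between-visit peak when the scheduled result exists, and the early termination visit falls 7–14 days after withdrawal, possibly after the peak.
- **The summaries include the maximum.** A reader might infer that the by-arm tables would look normal while patients crossed the criteria. An ALT of 8xULN at a protocol visit would be that arm's maximum. This stands, but a maximum looks the same for one such patient as for several.
- **The percentages are not losses.** It is tempting to read 79%, 58% and 25% as results lost to the SAP rule. An excursion that is never sampled is lost under any rule, and a repeat often follows an abnormal scheduled value that stays in the summary. The number actually excluded is unknown.
- **Adverse event tables are a by-arm route.** Protocol 8.2.2 and 9.1.1 make significant abnormalities, and those needing treatment or further evaluation, adverse events. SAP 5.7.1 tabulates TEAEs, serious TEAEs and those leading to discontinuation. This is a genuine but partial route, because it relies on investigator reporting and spreads events over preferred terms.
- **The SAP follows the protocol.** Protocol 11.3.6.4 also lists re-check values and summarises by time point. This is therefore a shared reporting gap, not a conflict between the documents.
- **Output 14.3.4.1 may help.** Its shell is in a separate document. Its section heading points to a per-patient listing, so a by-arm count is not something the SAP commits to.

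**Conclusion.** The point holds in a limited form. Apart from results mapped under SAP 5.3, unscheduled laboratory results stay out of the summaries, and no planned table gives by-arm counts for the numeric liver and renal criteria or worst post-baseline values. The planned output captures part of the information. It cannot give patient counts, joint ALT/AST–bilirubin events or, normally, persistence beyond two weeks.

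The number of patients affected cannot be derived from the documents. The only calculable figure is the spacing result: under uniform onset and assumed durations, 79%, 58% and 25% of 2-, 4- and 8-week excursions fall between scheduled samples over weeks 0–48. More than half do so only when the duration is below about 5 weeks. The conclusion does not depend on these figures. It rests on the list of outputs and on reading 14.3.4.1 as a listing.

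A reader might go further and infer that the plan hides a liver or renal signal. The documents do not support that, given the maxima, the mapping, the listings and the adverse event tables. This is a worthwhile, inexpensive improvement to safety reporting, and it does not touch the efficacy analyses.

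**What to change.** Keep the by-visit summaries on protocol visits, and add to SAP 5.7.2 and 10.3:

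1. **A by-arm count of patients** in the safety population who, at any post-baseline time including unscheduled and repeat samples, meet the numeric laboratory component of each liver and renal criterion already in protocol 6.5. For the two criteria that also need symptoms, label the row as the laboratory component only. Derive creatinine clearance by Cockcroft-Gault from serum creatinine and the most recent weight (scheduled after baseline at weeks 24, 48 and 72). State how persistence is derived from dated results. Use patients with at least one relevant post-baseline value as the denominator.
2. **By-arm shift tables** from baseline to worst post-baseline value (low, normal, high). Include platelets and neutrophils here rather than in the count, because the protocol gives no numeric cut-off for them.
3. **One sentence on scope**, stating that the SAP 5.3 mapping governs only the by-visit summaries.

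The cost is two displays, a clearance derivation and a few written rules, using data already collected. No clinical criterion changes. The downside is that unscheduled tests are triggered by abnormal results, so the new tables will run higher than the by-visit ones and should be labelled accordingly. The additions should be fixed before unblinding.
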